2 STUDY OVERVIEW

This is a double-blind, placebo-controlled, randomized, multicenter, global Phase 2 study comparing the efficacy and safety of single-agent poly (ADP-ribose) polymerase (PARP) inhibitor pamiparib to placebo as maintenance therapy in patients with advanced gastric cancer who have completed first-line platinum-based chemotherapy.

To be eligible for participation in the study, patients must have histologically confirmed adenocarcinoma of the stomach or gastroesophageal junction with inoperable locally advanced or metastatic disease. Patients must have achieved a partial response (PR) that is maintained for ≥ 4 weeks or complete response (CR) as determined by the investigator according to Response Evaluation Criteria in Solid Tumors (RECIST) Version 1.1 with platinum-based first-line chemotherapy.

All patients will be randomized within 8 weeks after the last platinum dose of first-line chemotherapy. Central interactive response technology will be used to randomize patients in a 1:1 ratio and assign eligible patients to 1 of 2 arms: Arm A – pamiparib or Arm B – Placebo. Patient randomization will be stratified by:

- HRD status (LOH_{high} versus LOH_{low} versus unknown)
- Region (China/Hong Kong/Taiwan versus Australia/Europe/North America versus Japan/South Korea versus rest of world [ROW])

- Eastern Cooperative Oncology Group (ECOG) performance status (0 versus 1)

3 STUDY OBJECTIVES

3.1 PRIMARY OBJECTIVES

- To evaluate the efficacy of maintenance therapy with pamiparib versus placebo in patients with inoperable locally advanced or metastatic gastric cancer with a CR or confirmed PR after first-line platinum-based chemotherapy, as measured by:
 - Progression-free survival (PFS) by RECIST Version 1.1 by investigator assessment

3.2 SECONDARY OBJECTIVES

- To further evaluate the efficacy of maintenance therapy with pamiparib versus placebo in patients with inoperable locally advanced or metastatic gastric cancer with a CR or confirmed PR after first-line platinum-based chemotherapy, as measured by:
 - Overall survival (OS)
 - Time to second subsequent treatment (TSST)
 - Objective response rate (ORR; CR or PR) by investigator assessment
 - Duration of response (DOR) by investigator assessment
 - Time to response by investigator assessment
- To evaluate safety and tolerability of pamiparib versus placebo, as measured by:
 - Incidence, timing, and severity of treatment-emergent adverse events (TEAEs), graded according to National Cancer Institute-Common Terminology Criteria for Adverse Events (NCI-CTCAE) Version 4.03 or higher

3.3 EXPLORATORY OBJECTIVES

- To confirm the PK of pamiparib, as measured by:
 - Lowest observed plasma concentrations (C_{trough}) at steady-state and plasma concentration two hours post-dose (C_{2h}) after a single dose and at steady-state for patients who received pamiparib
- To assess patient-reported outcomes on health-related quality of life, as measured by:
 - European Quality of Life 5-Dimensions 5-Levels Health Questionnaire (EQ-5D-5L)
 - European Organisation for Research and Treatment of Cancer Quality of Life Cancer Questionnaire (EORTC QLQ-C30)
 - EORTC QLQ gastric cancer module (EORTC QLQ-STO22)

- To explore potential biomarkers associated with the pharmacodynamics, response, and resistance to pamiparib:
 - Including, but not limited to, expression and mutations of genes in the DNA damage response pathway, LOH, and relationship to efficacy and resistance to pamiparib

4 STUDY ENDPOINTS

4.1 PRIMARY ENDPOINTS

PFS, defined as the time from randomization to progressive disease (PD) per RECIST Version 1.1 by investigator assessment or death due to any cause, whichever occurs first.

4.2 SECONDARY ENDPOINTS

Efficacy assessment:

- OS, defined as the time from randomization to death due to any cause
- Time to second subsequent treatment (TSST), defined as the time from randomization until the second subsequent anticancer therapy or death after next-line therapy
- ORR, defined as the proportion of patients with a best overall response of CR or PR per RECIST Version 1.1 by investigator assessment
- DOR, defined as the time from the first documented confirmed response of CR or PR to PD per RECIST Version 1.1 by investigator assessment or death due to any cause, whichever occurs first
- Time to response, defined as the time from randomization to the first documented response of CR or PR per RECIST Version 1.1 by investigator assessment

Safety assessment:

- Incidence, timing, and severity of TEAEs, graded according to NCI-CTCAE Version 4.03 or higher
- Safety and tolerability assessment of laboratory measurements, vital signs, and ECG findings

4.3 EXPLORATORY ENDPOINTS

Pharmacokinetics (PK) assessment:

- Lowest observed plasma concentrations (C_{trough}) at steady-state for patients who received pamiparib

Patient reported outcomes (PRO) assessments:

- European Quality of Life 5-Dimensions 5-Levels Health Questionnaire (EQ-5D-5L)
- European Organisation for Research and Treatment of Cancer Quality of Life Cancer Questionnaire (EORTC QLQ-C30)
- EORTC QLQ gastric cancer module (EORTC QLQ-STO22)

Biomarkers assessment associated with the pharmacodynamics, response, and resistance to pamiparib:

- Including, but not limited to, expression and mutations of genes in the DNA damage response pathway, LOH, and relationship to efficacy and resistance to pamiparib

5 SAMPLE SIZE CONSIDERATIONS

This study is designed to provide 80% power for PFS. The following assumptions are used in determining the sample size for this study:

- Overall type I error rate: 0.1 (1-sided)
- Randomization: 1:1
- Median PFS for placebo group: 6.0 months
- PFS hazard ratio (HR; pamiparib/placebo): 0.63

A sample size of approximately 128 patients (64 per treatment group) is required to achieve 85 PFS events within the planned study duration of approximately 26 months after the first patient is randomized to study, assuming an estimated accrual period of 20 months.

6 STATISTICAL METHODS

6.1 ANALYSIS SETS

Intent-to-Treat (ITT) Analysis Set includes all randomized patients who are assigned to study treatment (pamiparib or placebo). The ITT Analysis Set will be used for all efficacy analyses, except for endpoints ORR, DOR and time to response.

Safety Analysis Set includes all patients in the ITT Analysis Set who receive at least one dose of study treatment (pamiparib or placebo). The Safety Analysis Set will be used for all safety analyses.

Efficacy Evaluable Analysis Set includes all randomized patients who had measurable disease at baseline and had at least one post baseline tumor assessment unless discontinued treatment due to clinical progression or death prior to tumor assessment. The Efficacy Evaluable Analysis Set will be used for all efficacy analyses related to ORR, DOR and time to response by investigator assessment.

PK Analysis Set includes all patients who received pamiparib and contributed at least one plasma concentration.

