5.5.2. End of Treatment Visit

The EOT visit should occur within 7 days after BGB-290 or placebo has been permanently discontinued. Required assessments are listed in [Appendix 1](#). A visit should be scheduled as soon as possible, but the EOT visit may occur later after discussion with the medical monitor for specific circumstances, such as prolonged hospitalization. The visit at which tumor assessments showed PD may be used as the EOT visit providing all required assessments were performed. Tumor assessments do not have to be repeated if they were performed within 14 days of the EOT visit or at a prior response evaluation that documented PD. An ECG does not have to be repeated if it was performed within 14 days of the EOT visit.

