5.6.2. Long-term Follow-up

Patients will be followed for survival, further anticancer therapy, and diagnosis of MDS or AML via telephone contact or other means (eg, clinic visit) approximately every 12 weeks until death, withdrawal of consent, or the end of study, whichever occurs first ([Appendix 1](#)).

Patients who were permanently discontinued from study drug for reasons other than PD and meet criteria otherwise (eg, discontinued for AE and no new anticancer therapy) will be followed with tumor assessments every 8 weeks (± 7 days) until PD or any other reason listed in [Section 5.7](#), whichever occurs first. For efficacy assessments as per protocol, refer to [Section 7.3.2](#) and [Appendix 1](#). If the patient refuses to return for these tumor assessments or is unable to do so, every effort should be made to contact the patient by telephone to determine the patient's disease status and survival.

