10.1. Analysis Set

- Intent-to-Treat (ITT) Analysis Set includes all randomized patients who are assigned to study drug (BGB-290 or placebo). The ITT Analysis Set will be used for all efficacy analyses unless otherwise specified in the statistical analysis plan.
- Safety Analysis Set includes all patients in the ITT Analysis Set who receive any dose of study drug (BGB-290 or placebo). The Safety Analysis Set will be used for all safety analyses.
- Per-Protocol (PP) Analysis Set includes all patients in the ITT Analysis Set without major protocol deviations that impact assessment of efficacy. Criteria for exclusion from the PP Analysis Set will be determined and documented before the final analysis of PFS. The PP Analysis Set will be used to perform sensitivity analysis for the OS and PFS endpoints.

- PK Analysis Set includes all patients who receive BGB-290 and for whom valid BGB-290 PK parameters can be estimated.

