10.3.2. Secondary Efficacy Analyses

A secondary analysis of PFS will be conducted using the PP Analysis Set.

OS is the key secondary efficacy endpoint and is defined as the time from randomization to death due to any cause.

A stratified log-rank test incorporating the randomized stratification factors will be used to compare treatment groups using the ITT Analysis Set. The HR and its 2-sided 95% CI will be estimated using the stratified Cox-proportional hazards model. The median OS for each treatment group will be estimated using the Kaplan-Meier method and the 95% CI will be calculated using the Brookmeyer-Crowley method ([Brookmeyer and Crowley, 1982](#)).

A sensitivity analysis of OS will be conducted using the PP Analysis Set.

TSST is defined as the time from randomization until the second subsequent anti-cancer therapy or death after next-line therapy. Subjects alive and without the 2nd anti-cancer therapy will be censored at last known alive.

TSST will be assessed using a stratified log-rank test in ITT Analysis Set. The HR and its 2-sided 95% CI will be estimated using the stratified Cox-proportional hazards model. The median for each treatment group will be estimated using the Kaplan-Meier method and the 95% CI will be calculated using the Brookmeyer-Crowley method ([Brookmeyer and Crowley, 1982](#)).

ORR is defined as the proportion of patients with a best overall response of CR or PR per RECIST Version 1.1 by investigator assessment for the ITT Analysis Set. The ORR and its exact 2-sided 95% CI will be reported for each treatment group. A Cochran-Mantel-Haenszel score test will be used to compare treatment groups.

The best overall response will be summarized by the following categories for the ITT Analysis Set, patients with measurable disease at baseline and patients with nonmeasurable disease at baseline.

- CR
- PR (for the ITT Analysis Set and patients with measurable disease)

- Stable disease
- PD
- Not evaluable

DOR is defined as the time from the first documented confirmed response of CR or PR to PD per RECIST Version 1.1 by investigator assessment or death due to any cause, whichever occurs first. Only patients with response of CR or PR during the study will be included in duration of response analysis. The median duration of response and its 2-sided 95% CI for each treatment group will be provided.

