APPENDIX 1. SCHEDULE OF ASSESSMENTS

Study Phase	Screening ^a	Treatment ^b					Un-scheduled Visit ^c	End of treatment (EOT) Visit ^d	Safety Follow-up ^e	Long-term Follow-up ^f
		Cycle 1		Cycle 2		Cycle ≥3				
Day of Phase	-28 to -1	Day 1	Day 15	Day 1	Day 15	Day 1				
Allowed time window			± 2	± 3	± 3	± 3				
Study Day	-28 to -1	1	15	29	43	57, 85, etc.	Varies	Varies	Varies	Varies
CT with IV contrast of chest, abdomen and pelvis ^k	X (-14 to -1)					X (q8w ±7d)	X	X		X (q8w ±7d)
PET or bone scan, if clinically indicated ^l	X (-14 to -1)					X (q8w ±7d) ^l	X	X ⁿ		X (q8w ±7d) ^l
MRI scan of brain, if clinically indicated ^m	X					X (q8w ±7d) ^m	X	X ^o		X (q8w ±7d) ^m
Patient registration and randomization via IRT	X ^a									
BGB-290 or placebo		Twice daily dosing continuously								
Study drug dispensing/accountability		X		X		X	X	X		
Adverse events ⁿ	X	X	X	X	X	X	X	X	X	X
Concomitant medication(s) ^o	X	X	X	X	X	X	X	X	X	X (~q12w)
Pharmacokinetics ^p		X	X							
Blood for biomarkers ^q		X		X		X ^q (C4 only)		X		
Tumor tissue ^r	X									
Survival follow-up ^s										X (~q12w)

Abbreviations: -7/-14/-28 to -1, Day -7/-14/-28 to Day -1 (day of randomization) of screening; AE, adverse event; BID, twice daily; C, Cycle; CT, computed tomography; D, day; ECG, electrocardiogram; ECOG, Eastern Cooperative Oncology Group; eCRF, electronic case report form; EORTC QLQ-C30, European Organisation for Research and Treatment of Cancer Quality of Life Cancer Questionnaire; EORTC QLQ-STO22, European Organisation for Research and Treatment of Cancer Quality of Life gastric cancer module; EOT, end of treatment; EQ-5D-5L, European Quality of Life 5-Dimensions 5 Levels Health Questionnaire; HRD, homologous recombination deficiency; IRT, interactive response technology; IV, intravenous; MRI, magnetic resonance imaging; NCI-CTCAE; National Cancer Institute-Common Toxicity Criteria for Adverse Events; PARP, poly (ADP-ribose) polymerase; PD, progressive disease; PET, positron-emission tomography; PK, pharmacokinetic; PO, oral; q8w ±7d, every 8 weeks ±7 days; ~q12w, approximately every 12 weeks;

RECIST, Response Evaluation Criteria in Solid Tumors; SAE, serious adverse event.

- a. Screening must occur within 28 days of randomization. Some assessments have a narrower screening window as shown in the table. Assessments obtained within 7 days of Day 1 do not have to be repeated on Day 1. Patient registration and randomization may occur as late as Day 1 before any study treatment.

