3	No event of interest when analysis	Last available date from the following for patient with EOT: 1) EOT date 2) Last long-term followup visit date 3) Post-treatment anticancer treatment date Or cutoff date for patient on treatment	Censored

Objective Response Rate (ORR) by investigator assessment

ORR is defined as the proportion of patients with a best overall response of CR or PR per RECIST Version 1.1 by investigator assessment for the Efficacy Evaluable Analysis Set, before data cutoff or initiation of the next line of anticancer therapy, whichever comes first. The number and proportion of patients who achieve CR or PR according to both RECIST 1.1 will be summarized. Patients without postbaseline tumor assessment will be considered as non-responders. The ORR and its exact 2-sided 95% CI will be reported for each treatment group. A

Cochran-Mantel-Haenszel score test will be used to compare treatment groups. Confirmation of CR and PR are not required in this randomized study per RECIST v1.1.

The best overall response (BOR) will be summarized by the following categories for the Efficacy Evaluable Analysis Set. Patients without post-baseline disease assessment should be considered non-responders.

- Complete response
- Partial response
- Stable disease
- Progressive disease
- Not evaluable / Not evaluated

Duration of Response (DOR)

DOR is defined as the time from the first documented confirmed response of CR or PR to PD per RECIST Version 1.1 by investigator assessment or death due to any cause, whichever occurs first. Only patients with CR or PR during the study will be included in duration of response analysis. Censoring rule for DOR will follow PFS censoring rule.

The median and other quartiles of duration of response and its 2-sided 95% CI for each treatment group will be provided. Kaplan-Meier curve will be used to estimate median time and 95% CI for duration of response.

Waterfall plots will be provided for the maximum tumor shrinkage based on target lesion. The maximum tumor shrinkage based on target lesion used in the plots will be listed. These analyses will be performed based on RECIST 1.1.

Time to response by investigator assessment

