8 CHANGES IN THE PLANNED ANALYSIS

- The Per-Protocol (PP) analysis set defined in the protocol BGB-290-303 (version 1.0, 2020-02-13) will not be considered in the analysis.
- Progression-free survival 2 (PFS2) by investigator assessment as secondary efficacy endpoints defined in the protocol BGB-290-303 (version 1.0, 2020-02-13) will not be considered in the analysis.
- Confirmation of response will not be required for ORR in randomized clinical studies per RECIST v1.1. No confirmation of response required for the analysis of DOR and Time to response to be consistent with analysis of ORR.
- The stratification factor of HRD status (LOH_{high} versus LOH_{low} versus unknown) will not be included as strata for PFS, OS, and TSST nor covariate in primary or secondary analyses due to high rate of patients with unknown LOH reported. And the Region will have three strata (China/Hong Kong/Taiwan versus Australia/Europe/North America versus Japan/South Korea/rest of world [ROW]) for PFS, OS, TSST, and covariate in primary or secondary analyses after combining patients in Japan/South Korea with patients in ROW as small number of patients were enrolled in Japan and no patients were enrolled in South Korea.
- No PK parameters will be derived and reported in clinical study report. The definition of PK analysis set is thus modified as all patients who have at least one plasma concentration.

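### The SAP tests ORR on a set that requires a post-baseline scan, so patients left unscanned for reasons other than clinical progression or death leave the denominator; Section 8 does not record this change from ITT

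*SAP*

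**What the plan says.** Protocol 10.3.2 defines ORR as the proportion with a best overall response of CR or PR "by investigator assessment for the ITT Analysis Set", compared between arms with a Cochran-Mantel-Haenszel (CMH) score test. Protocol 10.1 leaves room for change: "The ITT Analysis Set will be used for all efficacy analyses unless otherwise specified in the statistical analysis plan".

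SAP 6.1 uses that room. It takes ORR, duration of response and time to response off ITT and puts them on an Efficacy Evaluable set. Entry needs measurable disease at baseline and a second condition, that the patient "had at least one post baseline tumor assessment unless discontinued treatment due to clinical progression or death prior to tumor assessment". SAP 6.4.2 then defines ORR and best overall response on this set, keeps the CMH test, and adds: "Patients without postbaseline tumor assessment will be considered as non-responders".

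SAP Section 8 lists the departures from the protocol. It covers two other analysis sets (Per-Protocol dropped, PK redefined) and one change to ORR itself: "Confirmation of response will not be required for ORR in randomized clinical studies per RECIST v1.1". The change of ORR population is not there.

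**The concern.** The two entry conditions differ in kind. Measurable disease is known before randomization, so restricting to it leaves the arms comparable. Whether a patient is ever scanned afterwards is a post-randomization outcome that treatment can influence.

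Only clinical progression or death excuses a missing scan. A patient never scanned after stopping for an adverse event, withdrawing or being lost to follow-up is removed rather than counted as a failure. The non-responder sentence in SAP 6.4.2 looks like a safeguard, but it operates inside a set that has already excluded these patients. It can reach only the clinical-progression and death exceptions.

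At stake is a formally tested secondary comparison whose denominator depends partly on what happened on treatment, with no other ORR analysis in the SAP that keeps these patients. A higher unscanned share on pamiparib (BGB-290) is plausible but not shown in the documents, and the bias could run either way.

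**Working it through.** **Plan figures.** The documents give no expected ORR and no unscanned rate, so there is no ORR figure to reproduce. The one design calculation, 85 PFS events (HR 0.63, one-sided alpha 0.10, 80% power, 1:1), reproduces by Schoenfeld's formula: 4 × (1.2816 + 0.8416)² / (ln 0.63)² = 84.5, rounded up to 85. It does not depend on the ORR set.

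**Who is excluded.** The protocol limits the group in two ways.
- The schedule in Appendix 1 marks "CT with IV contrast of chest, abdomen and pelvis" at the end-of-treatment visit, and Section 5.5.2 waives it only when recent imaging or documented PD exists: "Tumor assessments do not have to be repeated if they were performed within 14 days of the EOT visit".
- Section 5.6.2 keeps scanning patients who stop drug without PD, for example those "discontinued for AE and no new anticancer therapy) will be followed with tumor assessments every 8 weeks".

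Most adverse-event stops therefore stay in the set. The patients at risk are mainly premature study discontinuations, for whom Sections 5.5.1 and 5.7 foresee no end-of-treatment or follow-up visit, before a first scan at about week 8.

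**Formula.** Let d be the share of an arm's measurable patients excluded as never scanned. They contribute no responders, so

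reported ORR = ORR / (1 − d),

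where ORR on the right counts never-scanned patients as non-responders, the convention SAP 6.4.2 itself states.

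**By share, assuming ORR 20% in both arms (no real difference):**

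| d, pamiparib | d, placebo | Reported rates | Difference (points) |
|---|---|---|---|
| 5% | 5% | 21.05 vs 21.05 | 0 |
| 5% | 2% | 20/0.95 = 21.05 vs 20/0.98 = 20.41 | +0.64 |
| 3/45 = 6.7% | 0% | 21.43 vs 20.00 | +1.43 |
| 10% | 2% | 20/0.90 = 22.22 vs 20.41 | +1.81 |
| 2% | 5% | 20.41 vs 21.05 | −0.64 |

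The 3/45 row uses the only anchor in the documents, the patients who stopped for an adverse event in the Phase 1 study (Protocol 1.4.2.3). One of those stops was for cutaneous metastases, and the figure equals d only if none of the three was ever scanned.

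**By count, assuming 40 measurable patients and 8 responders per arm:** 8/40 = 20.00%, 8/39 = 20.51%, 8/37 = 21.62%. Excluding 1 vs 0 gives +0.51 points, 3 vs 1 gives +1.11, 3 vs 0 gives +1.62, and 1 vs 3 gives −1.11.

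**Dependence on the assumed ORR.** The shift is proportional to it. For 10% vs 2% excluded the factor is 1/0.90 − 1/0.98 = 0.0907, so 1.8 points at ORR 20%, 0.9 at 10% and 0.45 at 5%.

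**Effect on the test.** These cases assume 64 per arm, all measurable, and an unstratified CMH test.

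| Responders | Excluded | Difference (points) | p |
|---|---|---|---|
| 10 vs 5 | none | 7.8 | 0.171 |
| 10 vs 5 | 6 vs 2 | 9.2 | 0.130 |
| 13 vs 6 | none | 10.9 | 0.083 |
| 13 vs 6 | 6 vs 2 | 12.7 | 0.057 |
| 13 vs 6 | 10 vs 3 | 14.2 | 0.041 |
| 16 vs 8 | none | 12.5 | 0.071 |
| 16 vs 8 | 6 vs 2 | 14.7 | 0.045 |

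Balanced exclusions of 3 vs 3 barely move p (0.171 to 0.170 for 10 vs 5). An imbalance can carry a borderline result across 0.05.

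**The case against.** The strongest reply is that the change is permitted and visible. Protocol 10.1 allows another set and SAP 6.1 names the endpoints and defines the set. That stands: this is not a forbidden or hidden switch. But the change departs from an explicit ITT definition, and Section 8 records comparable changes while omitting this one.

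A second point is that calling the rates overstated depends on a convention. If missing scans were unrelated to response, the evaluable-set rate would estimate response probability without bias. That is also true. However, the non-responder convention follows from the protocol's ITT definition, SAP 6.4.2 states it, and it keeps the randomized comparison intact.

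Third, the effect is small against the endpoint's precision. With 40 per arm and ORR 20%, the 95% half-width for the difference is 1.96 × √(2 × 0.2 × 0.8/40) = 17.5 points, about ten times the 1.8-point shift. ORR is also an unpowered secondary endpoint. This limits the importance of the point but gives no reason to keep the condition.

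Finally, the measurable-disease condition may remove more patients, since patients enter in response and measurable disease is not an entry criterion. If 75% or 50% were measurable (an assumption), 64 per arm becomes 48 or 32, and 10 responders, all measurable, would read 20.8% or 31.25% instead of 15.6%. That changes what the rate means, and it too should be disclosed. It is fixed at baseline, so it does not bias the comparison as the scan condition can.

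**Conclusion.** The concern holds. Requiring a post-baseline scan selects the ORR population partly on a post-randomization outcome, disables the SAP's own non-responder rule for the patients who most need it, and is not listed among the changes from the protocol.

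The size is probably small: about 0 to 2 points in either direction for the excluded shares and counts considered at an ORR of 20%, and less at a lower ORR. The ORR, the number with measurable disease and the excluded shares are all assumptions, so the documents cannot confirm that it is small.

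The between-arm bias arises only if the excluded shares differ. The primary PFS analysis, OS and TSST remain on ITT and are unaffected. The scan condition removes no responder from duration of response or time to response, because a responder has necessarily been scanned.

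**What to change.** In SAP 6.1, define the main ORR and best-overall-response population as all randomized patients with measurable disease at baseline. Count every patient with no post-baseline assessment, whatever the reason, as a non-responder in the not-evaluable category. The non-responder sentence in SAP 6.4.2 then does what it says. Keep the Efficacy Evaluable set as a sensitivity analysis at most.

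In SAP Section 8, add a bullet recording the move from ITT, including the restriction to measurable disease.

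The cost is one sentence and one bullet, with no new data. The reported ORR will be slightly lower wherever patients were never scanned.
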